9.1.3.1 BICR Confirmation of Radiographic Progression

Sites should submit all scans to the imaging core lab on a rolling basis, throughout the duration of the study. BICR of scans will occur on a rolling basis, blinded to treatment arm, clinical data, and investigator assessment of submitted scans. When radiographic progression per RECIST 1.1 or RANO criteria is assessed by the investigator, the site will inform the imaging core lab, in order for BICR assessment of progression to be performed. The BICR review will be completed and the results provided to the site as specified in the imaging vendor documents, provided there are no pending imaging queries to the site. All details on the timelines and associated process requirements will be outlined in the Imaging Manual. Participants whose RECIST 1.1 or RANO radiographic progression is not confirmed by the BICR will be required to continue tumor assessments (if clinically feasible) according to the protocol-specified schedule, or sooner if clinically indicated. Also, if participants discontinue treatment without radiographic progression, tumor assessments will continue according to the protocol specified schedule, as noted in [Section 2](#) (Schedule of Activities) until progression has been confirmed by BICR. All study treatment

decisions will be based on the investigator's assessment of tumor images and not on the BICR assessment.

BICR confirmation of disease progression is mandatory for participants in Arm B (nivolumab monotherapy) prior to enrolling in Arm B rollover to receive treatment with nivolumab in combination with ipilimumab. The participant will be re-baselined based on the investigator's assessment of the scans with which BICR progression was confirmed. Tumor assessments in participants in rollover cohort will be done by BICR and should comply with the requirements outlined in this protocol.

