3.1.4.1 Rationale for Independent Central Review

The primary endpoint of ORR will be based on centrally-assessed radiologic tumor measurements (and additional clinical indicators, where applicable) using standard disease-specific response criteria. A centrally-assessed ORR will provide standardized assessment of progression and response using disease-specific response criteria. For this purpose, radiologic imaging from this study will be transmitted to an imaging core lab for analysis by a Blinded Independent Central Review (BICR) committee. Please see [Section 9.1](#) and CA209848 Imaging Manual for additional information.

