5.1.1.2 Blinded Independent Central Review Committee

A Blinded Independent Central Review (BICR) Committee will be formed for standardized response assessment. Images will be submitted to an imaging third-party vendor for central review.

Imaging acquisition guidelines and submission process will be outlined in the CA209848 Study Imaging Manual to be provided by the vendors. For tumor types which require clinical indicators as part of the standard response assessment, the clinical indicator data will be provided to the BICR along with imaging data.

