9.1 Efficacy Assessments

Efficacy will be based on imaging assessments. For solid tumors, response will be assessed using RECIST 1.1 for solid tumors (see [appendix 7](#)). For CNS tumors, response will be assessed using RANO 2010 criteria⁵³ supplemented by clinical neurologic examination and performance status, as well as additional considerations as applicable e.g. adverse events or steroid requirement. (See [Appendix 8](#)).

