9.1.3 Imaging and Clinical Assessment

Tumor assessments should continue even if dosing is delayed or discontinued. Changes in tumor measurements and tumor responses will be assessed by the same investigator. Investigators will report the number and size of new lesions that appear while on study. Assessments of PR and CR must be confirmed at least 4 weeks (28 days) after initial response. A Best Overall Response of SD requires a minimum of 77 days on study from date of first dose to the date of the first imaging assessment.

For participants with CNS malignancy, RANO 2010 criteria will be used.

Table 9.1.3-1: RANO Criteria for Time-point Response Assessment Incorporating MRI and Clinical Factors

Response	Criteria
CR	Requires all of the following: complete disappearance of all enhancing measurable and nonmeasurable disease; no new lesions; stable or improved nonenhancing (T2/FLAIR) lesions; participants must be off corticosteroids (or on physiologic replacement doses only); and stable or improved clinically. Note: Participants with nonmeasurable disease only cannot have a complete response; the best response possible is stable disease.
PR	Requires all of the following: $\geq 50\%$ decrease compared with baseline in the sum of products of perpendicular diameters (SPD) of all measurable enhancing lesions; no progression of nonmeasurable disease; no new lesions; stable or improved nonenhancing (T2/FLAIR) lesions on same or lower dose of corticosteroids compared with baseline scan; the corticosteroid dose at the time of the scan evaluation should be no greater than the dose at time of baseline scan; and stable or improved clinically. Note: Participants with nonmeasurable disease only cannot have a partial response; the best response possible is stable disease.
SD	Requires all of the following: does not qualify for complete response, partial response, or progression; stable nonenhancing (T2/FLAIR) lesions on same or lower dose of corticosteroids compared with baseline scan. In the event that the corticosteroid dose was increased for new symptoms and signs without confirmation of disease progression on neuroimaging, and subsequent follow-up imaging shows that this increase in corticosteroids was required because of disease progression, the last scan considered to show stable disease will be the scan obtained when the corticosteroid dose was equivalent to the baseline dose.

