Table 9.1.3-1: RANO Criteria for Time-point Response Assessment Incorporating MRI and Clinical Factors

Response	Criteria
PD	Defined by any of the following: $\geq 25\%$ increase in sum of the products of perpendicular diameters of enhancing lesions compared with the smallest tumor measurement obtained either at baseline (if no decrease) or best response, on stable or increasing doses of corticosteroids (Stable doses of corticosteroids include participants not on corticosteroids); significant increase in T2/FLAIR nonenhancing lesions on stable or increasing doses of corticosteroids compared with baseline scan or best response after initiation of therapy not caused by comorbid events (eg, radiation therapy, demyelination, ischemic injury, infection, seizures, postoperative changes, or other treatment effects); any new lesion; clear clinical deterioration not attributable to other causes apart from the tumor (eg, seizures, medication adverse effects, complications of therapy, cerebrovascular events, infection, and so on) or changes in corticosteroid dose; failure to return for evaluation as a result of death or deteriorating condition; or clear progression of nonmeasurable disease.

Table 9.1.3-2: Assessment of Best Overall Response

Best Overall Response	Criteria ⁵⁴
CR	CR observed in assessments ≥ 4 weeks apart per RANO
PR	PR observed in assessments ≥ 4 weeks apart per RANO
SD	SD observed and does not qualify for CR or PR or Suspected PD followed with histologic results not confirming PD, and no CR, PR or SD observed
Note: To qualify for SD there must be a minimum on-treatment period of 6 weeks.)	
Not Evaluable (NE)	Insufficient data to determine disease progression or response
PD	No CR, PR, or SD prior to PD

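### Section 9.1.3.1 blinds the BICR to clinical data without exception, while the synopsis and Sections 3.1.4.1 and 5.1.1.2 have the BICR use the clinical indicators that RANO needs in primary CNS tumours

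*Combined protocol and SAP*

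**What the plan says.** The two sides of the conflict:

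- Section 9.1.3.1 (BICR Confirmation of Radiographic Progression): "BICR of scans will occur on a rolling basis, blinded to treatment arm, clinical data, and investigator assessment of submitted scans". The same paragraph names RANO, so primary CNS tumours fall within it, and no exception is stated.
- Section 5.1.1.2, repeated in the synopsis: for tumour types whose standard assessment needs clinical indicators, "the clinical indicator data will be provided to the BICR along with imaging data".
- Section 3.1.4.1 describes the central primary endpoint as resting on radiologic measurements ("and additional clinical indicators, where applicable) using standard disease-specific response criteria").

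The criteria the BICR has to apply in primary CNS tumours:

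- Section 9.1: RANO 2010, "supplemented by clinical neurologic examination and performance status, as well as additional considerations as applicable e.g. adverse events or steroid requirement".
- Table 9.1.3-1, CR: "participants must be off corticosteroids (or on physiologic replacement doses only); and stable or improved clinically".
- Table 9.1.3-1, PR: "the corticosteroid dose at the time of the scan evaluation should be no greater than the dose at time of baseline scan", together with stable or improved clinical status.
- Table 9.1.3-1, SD: "stable nonenhancing (T2/FLAIR) lesions on same or lower dose of corticosteroids compared with baseline scan". Clinical status is not in this row; Appendix 8 adds it.
- Table 9.1.3-1, PD: "Defined by any of the following", followed by a list in which some items need steroid or clinical information and others do not.

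Section 10.3.1 defines the primary endpoint from the best overall response determined by BICR, using RANO for primary CNS neoplasms.

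**The concern.** BICR-assessed ORR is the primary endpoint, and the sample size rests on the precision of its estimate, so the rate and its interval are the result of the trial. A reader who takes 9.1.3.1 at its word would see the scans but not the steroid dose or the participant's clinical condition. That reader could credit CR or PR to a participant whose enhancement shrank on a raised steroid dose, or who was clinically worse, although Table 9.1.3-1 excludes both.

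A second consequence concerns progression. Table 9.1.3-1 accepts clear clinical deterioration as PD. A BICR without clinical data could not confirm such a case, yet 9.1.3.1 makes BICR confirmation mandatory before Arm B rollover. Missing such a progression could also lengthen DOR or leave a later response countable.

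**Working it through.** **1. Which RANO categories depend on the data that 9.1.3.1 withholds**

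| Category | Steroid dose needed | Clinical status needed | Source |
|---|---|---|---|
| CR | yes | yes | Table 9.1.3-1, Appendix 8 |
| PR | yes | yes | Table 9.1.3-1, Appendix 8 |
| SD | yes | only in Appendix 8 | Table 9.1.3-1, Appendix 8 |
| PD | for some criteria | for some criteria | Table 9.1.3-1 |

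Within PD, a new lesion or clear progression of nonmeasurable disease needs neither item. Growth of enhancing or T2/FLAIR lesions is conditioned on stable or increasing steroids. Clinical deterioration needs clinical data. Appendix 8 adds that a steroid increase alone does not establish progression.

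**2. Direction**

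CR and PR require all of their conditions. Dropping the steroid and clinical conditions from them can therefore only add responders. The effect through PD has no fixed sign: a clinical progression could be missed, but growth on a reduced steroid dose could also be called PD and cut off a later response.

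**3. The plan's own figures**

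Section 10.1 gives exact 95% intervals for n = 76. The Clopper-Pearson limits for x responses are:

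- lower = the 0.025 quantile of Beta(x, 76 − x + 1)
- upper = the 0.975 quantile of Beta(x + 1, 76 − x)

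For x = 30 this gives 0.395 (0.284, 0.514); the plan prints 0.39 (0.28, 0.51). All ten rows of the table reproduce to two decimals.

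**4. Possible size**

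Inputs from the plan: n = 76 per TMB population and a cap of approximately 15% per tumour type (Section 10.1). Assumptions: primary CNS tumours count as one tumour type, and 0 to 3 responses are misclassified. The documents give no figure for either.

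- Ceiling on CNS participants: 0.15 × 76 = 11.4, so about 11.
- Effect of one misclassified response: 1/76 = 1.3 percentage points.

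| Responses wrongly credited among 30 | Correct count | ORR | Exact 95% CI |
|---|---|---|---|
| 0 | 30/76 | 39.5% | 28.4% to 51.4% |
| 1 | 29/76 | 38.2% | 27.2% to 50.0% |
| 2 | 28/76 | 36.8% | 26.1% to 48.7% |
| 3 | 27/76 | 35.5% | 24.9% to 47.3% |

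At three cases the estimate moves by 39.5 − 35.5 = 4.0 points from the rounded values (3/76 = 3.9 exactly), and the lower limit by 28.4 − 24.9 = 3.5 (3.6 before rounding).

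**The case against.** The strongest reply is that the sections can be read together. Section 9.1.3.1 is headed as a procedure for confirming radiographic progression, and its blinding phrase is a general guard against bias. Section 5.1.1.2 sets up the BICR committee and makes the specific provision for tumour types that need clinical indicators. The synopsis repeats it, and Section 3.1.4.1 agrees. On that reading the specific provision governs, CNS cases are read under full RANO, and nothing is biased. The Imaging Manual, to which both sections defer for detail, may already say so; it is not among the documents.

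Much of this stands. A reader might infer that the primary endpoint cannot be assigned as defined in primary CNS tumours. The documents do not support that, because three places provide for the clinical indicators. A reader might also infer that 9.1.3.1 overrides 5.1.1.2; nothing says so. Nor does every RANO category need both steroid dose and clinical status, as the first table shows.

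What does not fall away is the conflict itself. Section 9.1.3.1 covers RANO by name, excludes clinical data without qualification, and does not refer to 5.1.1.2. The reconciling reading is reasonable, but the reader has to supply it.

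**Conclusion.** The contradiction is real and sits in current text governing how the primary endpoint and the mandatory confirmation of progression are read. It is firmest for CR and PR, which determine ORR.

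It would be wrong to conclude that ORR is inflated. Any inflation depends on CNS scans having been read without steroid and clinical data, and the documents do not show that this happened. If 5.1.1.2 is followed, the effect is zero. If 9.1.3.1 is followed literally, each wrongly credited response adds 1.3 points. The range of 0 to 3 cases is an assumption, and the ceiling of about 11 CNS participants assumes that primary CNS tumours count as one type under an approximate cap.

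The rollover consequence is also conditional on clinical data being withheld. It concerns Arm B, whereas the primary endpoint concerns the combination arm. The point is modest in size, affects one capped tumour group and changes no design figure, but should be settled before the primary analysis.

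**What to change.** Reconcile Section 9.1.3.1 with Section 5.1.1.2. Suggested wording for 9.1.3.1: *The BICR is blinded to treatment arm, to investigator assessment, and to clinical data other than the clinical indicators that RANO requires (corticosteroid dose and clinical/performance status), which are supplied under Section 5.1.1.2.* Align the Imaging Manual with it.

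Before the primary analysis, confirm that primary CNS cases were read with these data, and re-read only any that were not. The passages bearing on BICR confirmation before Arm B rollover need to be reconciled with the PD definition in Table 9.1.3-1; no rollover rule is proposed here.

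The cost is one sentence, alignment of the Imaging Manual and possibly a few re-reads. Concomitant medication and performance status are already scheduled in Tables 2-2 to 2-4, so no new study procedure should be needed.

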9.2 Adverse Events

The definitions of an AE or serious adverse event (SAE) can be found in [Appendix 3](#).

AEs will be reported by the participant (or, when appropriate, by a caregiver, surrogate, or the participant's legally authorized representative).

The investigator and any designees are responsible for detecting, documenting, and reporting events that meet the definition of an AE or SAE and remain responsible for following up AEs that are serious, considered related to the study treatment or the study, or that caused the participant to discontinue before completing the study.

Contacts for SAE reporting specified in [Appendix 3](#).

Immune-mediated adverse events are AEs consistent with an immune-mediated mechanism or immune-mediated component for which non-inflammatory etiologies (e.g. infection or tumor progression) have been ruled out. IMAEs can include events with an alternate etiology which were exacerbated by the induction of autoimmunity. Information supporting the assessment will be collected on the participant's case report form.

9.2.1 Time Period and Frequency for Collecting AE and SAE Information

The collection of non-serious AE information (with the exception of non-serious AEs related to SARS-CoV-2 infection) should begin at initiation of study treatment and for a minimum of 100 days following discontinuation of study treatment and at the timepoints specified in the Schedule of Activities ([Section 2](#)).

Sections 5.6.1 and 5.6.2 in the Investigator Brochure (IB) represent the Reference Safety Information to determine expectedness of serious adverse events for expedited reporting.

Following the participant's written consent to participate in the study, all SAEs, whether related or not related to study drug, must be collected, including those thought to be associated with protocol-specified procedures.

All SAEs and all AEs (SAEs and non-serious AEs) associated with confirmed or suspected SARS-CoV-2 infection must be collected from the time of signing the consent, including those thought to be associated with protocol-specified procedures and until 100 days following discontinuation of dosing.

Note: for participants who signed a pre-screening consent with submission of an archived tumor sample for eligibility assessment, SAE collection will start at the time of signature of the full informed consent. For participants who signed a pre-screening consent to agree to collection of a fresh biopsy, SAE collection will start at the time of signature of the pre-screening informed consent.

For participants randomized and never treated with study drug, SAEs should be collected for 30 days from the date of randomization.

The investigator must report any SAE that occurs after these time periods and that is believed to be related to study drug or protocol-specified procedure, (eg, a follow-up skin biopsy).

- Medical occurrences that begin before the start of study treatment but after obtaining informed consent will be recorded on the appropriate section of the eCRF module.
- All SAEs will be recorded and reported to Sponsor or designee within 24 hours, as indicated in [Appendix 3](#).
- The investigator will submit any updated SAE data to the sponsor or designee within 24 hours of updated information being available.

Investigators are not obligated to actively seek AEs or SAEs in former study participants. However, if the investigator learns of any SAE, including a death, at any time after a participant has been discharged from the study, and he/she considers the event reasonably related to the study treatment or study participation, the investigator must promptly notify the sponsor.

The method of evaluating, and assessing causality of AEs and SAEs and the procedures for completing and reporting/transmitting SAE reports are provided in Appendix 3.

9.2.2 Method of Detecting AEs and SAEs

Adverse events can be spontaneously reported or elicited during open-ended questioning, examination, or evaluation of a participant. Care should be taken not to introduce bias when collecting AE and/or SAEs. Inquiry about specific AEs should be guided by clinical judgement in the context of known adverse events, when appropriate for the program or protocol.

All nonserious adverse events (not only those deemed to be treatment-related) should be collected continuously during the treatment period and for a minimum of 100 days following discontinuation of study treatment.

Every adverse event must be assessed by the investigator with regard to whether it is considered immune-mediated. For events which are potentially immune-mediated, additional information will be collected on the participant's case report form.

9.2.3 Follow-up of AEs and SAEs

- Nonserious AEs should be followed to resolution or stabilization, or reported as SAEs if they become serious (see Appendix 3).
- Follow-up is also required for nonserious AEs that cause interruption or discontinuation of study treatment and for those present at the end of study treatment as appropriate.

- All identified nonserious AEs must be recorded and described on the nonserious AE page of the CRF (paper or electronic). Completion of supplemental CRFs may be requested for AEs and/or laboratory abnormalities that are reported/identified during the course of the study.

After the initial AE/SAE report, the investigator is required to proactively follow each participant at subsequent visits/contacts. All SAEs, non-serious AEs of special interest (as defined in [Section 9.2](#)), and AEs (SAEs and non-serious AEs) associated with confirmed or suspected SARS-CoV-2 infection will be followed until resolution, until the condition stabilizes, until the participant is lost to follow-up (as defined in [Section 8.3](#)), or until SARS-CoV-2 infection is ruled out.

Further information on follow-up procedures is given in [Appendix 3](#).

9.2.4 Regulatory Reporting Requirements for SAEs

- Prompt notification by the investigator to the Sponsor of SAEs is essential so that legal obligations and ethical responsibilities towards the safety of participants and the safety of a product under clinical investigation are met.
- An investigator who receives an investigator safety report describing SAEs or other specific safety information (eg, summary or listing of SAEs) from the Sponsor will file it along with the Investigator Brochure and will notify the IRB/IEC, if appropriate according to local requirements.

Sponsor or designee will be reporting adverse events to regulatory authorities and ethics committees according to local applicable laws including European Directive 2001/20/EC and FDA Code of Federal Regulations 21 CFR Parts 312 and 320. A SUSAR (Suspected, Unexpected Serious Adverse Reaction) is a subset of SAEs and will be reported to the appropriate regulatory authorities and investigators following local and global guidelines and requirements.

All SAEs must be collected that occur during the screening period and within 100 days of the last dose of study treatment. For participants randomized/assigned to treatment and never treated with study drug, SAEs should be collected for 30 days from the date of treatment assignment.

9.2.5 Pregnancy

If, following initiation of the study treatment, it is subsequently discovered that a participant is pregnant or may have been pregnant at the time of study exposure, including during at least 5 half-lives after product administration, the investigator must immediately notify the BMS Medical Monitor/designee of this event and complete and forward a Pregnancy Surveillance Form to BMS Designee within 24 hours of awareness of the event and in accordance with SAE reporting procedures described in [Appendix 3](#).

If the investigator determines a possible favorable benefit/risk ratio that warrants continuation of study treatment, or re-initiation of study treatment, a discussion between the investigator and the BMS Medical Monitor/designee must occur. If, for whatever reason, the pregnancy has ended, confirmed by negative serum pregnancy test, treatment may be resumed (at least 3 weeks and not

greater than 6 weeks after the pregnancy has ended), following approvals of participant /sponsor /IRB/EC, as applicable.

Follow-up information regarding the course of the pregnancy, including perinatal and neonatal outcome and, where applicable, offspring information must be reported on the Pregnancy Surveillance Form.

